#### 5.0 STUDY MATERIALS

#### 5.1 Device Description

The Carpentier-Edwards PERIMOUNT Magna Mitral and Magna Mitral Ease valves included in this study are modified versions of the Carpentier-Edwards PERIMOUNT mitral valve models 6900, 6900P and 6900PTFX. All study valves are built upon the same proven wireform frame and leaflet attachment as the Model 6900 and are available in various sewing ring diameters and sizes shown below in Table 3.

Tissue Annulus Diameter (TAD)	28	29.5	31.5	33.5	33.5
Model 7000/7000TFX	25	27	29	31	33
Model 7200TFX	27	29	31	33	35
Model 7300/7300TFX	25	27	29	31	33

Table 4. Valve Size by Tissue Annulus Diameter (mm)

These bioprostheses incorporate a sewing ring specifically designed for the mitral position and are the first bioengineered mitral valve design with three selected bovine pericardial leaflet mounted on a flexible metal alloy frame.

Bovine pericardium was selected for its intrinsic properties for valve manufacture, notably in terms of collagen content and tolerance to high bending curvatures. Bovine pericardium is cross-linked using a Neutralogic fixation process in which tissue is treated in a stress-free bath of buffered glutaraldehyde solution. Magna Mitral valve models 7000TFX, 7200TFX and 7300TFX are treated according to the ThermaFix process, which involves heat treat of the tissue in glutaraldehyde and uses ethanol and Polysorbate-80 (a surfactant). Glutaraldehyde has been shown to reduce the antigenicity

This document and the information contained herein is considered Proprietary and Confidential and may not be reproduced, used or disclosed without written permission from Edwards Lifesciences LLC.

of tissue xenograft valves and increase tissue stability. Glutaradehyde alone has not been shown to affect or reduce the calcification rate of the valve. .

Tissue thickness is measured for each valve size and leaflets are die-cut in selected areas of the pericardial sheet. Three leaflets matched for similar thickness and elasticity are then assembled and mounted underneath the lightweight wireform frame, to minimize commissural stress points. The lightweight wireform frame is made of corrosion resistant cobalt-chromium ally, chosen for its spring efficiency and fatigue properties. The frame is designed to be compliant at the orifice as well as at the commissures. The frame is covered with a woven polyester fabric sewn with polyfluoroethylene thread. The wireform frame is symmetrical and the three commissure supports (struts) are equally spaced. Detailed instructions for use of the valve including a description of the sewing ring and valve holder system can be found for each Magna mitral valve model in Appendix 4.

#### **Comparison of Mitral Valve and Packaging Systems**

System Feature	Carpentier-Edwards PERIMOUNT Magna Mitral 7000 / 7000TFX	Carpentier-Edwards PERIMOUNT Magna Mitral Ease 7200TFX	Carpentier-Edwards PERIMOUNT Magna Mitral Ease 7300 / 7300TFX
-------------------	---	---	---

System Feature	Carpentier-Edwards PERIMOUNT Magna Mitral 7000 / 7000TFX	Carpentier-Edwards PERIMOUNT Magna Mitral Ease 7200TFX	Carpentier-Edwards PERIMOUNT Magna Mitral Ease 7300 / 7300TFX
Valve	Carpentier-Edwards PERIMOUNT Magna Mitral pericardial bioprosthesis, model 7000TFX sizes 25 – 33 mm	Valve is identical to the model 7000TFX Valve, but has a different sizing convention; sizes 27 – 35	Valve is identical to the model 7000TFX valve, sizes 25 – 33 mm. A black silk suture guide line is added to the sewing ring
Clip	Acetal Homopolymer	Acetal Homopolymer	Acetal Homopolymer Clip contains new features for sleeve engagement and blue arrow molded into material.
Jar	3.8 oz Jar	3.8 oz Jar	3.8 oz Ribbed Jar Internal Ribs added to 3.8 oz Jar
Sleeve	Polypropylene Sleeve	Polypropylene Sleeve	Polypropylene Ribbed Sleeve External Ribs added to Sleeve
Holder System	Tricentrix Holder System: White * Holder White Post White Adapter *White also referred to as Natural	Grey Tricentrix Holder System: Grey Holder Grey Post White Adapter	Tri-color Tricentrix Holder System: Grey Holder White Post Blue Adapter Component color changed to provide additional contrast
Accessories Handle Class I Sizers Class Ila Tray Class I NB: TÜV SÜD Product Service GmbH CE 0123	Handles 1111, 1117 Sizer 1177HP Tray TRAY1177HP	Flex Handle 1172 Replica Sizer 1171R Barrel Sizer 1171B Tray SET 1171	Flex Handle 1173 Replica Sizer 1173R Barrel Sizer 1173B Tray SET 1173 Updated graphics and size markings on sizers and tray

# 5.2 **Pre-Clinical Studies**

Pre-clinical bench studies included sewing ring integrity testing, spot weld pull test and chromium-cobalt band compression resistance testing, valve hydrodynamic, durability and structural integrity testing, shelf life & packaging and biocompatibility testing. All testing met acceptance criteria per ISO 5840 and FDA Heart Valve Guidance 1996.

This document and the information contained herein is considered Proprietary and Confidential and may not be reproduced, used or disclosed without written permission from Edwards Lifesciences LLC.

# 6.0 STUDY PROCEDURES

Edwards will provide the study sites with the post approval study clinical protocol, case report forms (CRFs) (Appendix 5), Quality of Life survey (Appendix 6) and all other necessary study related documentation. Edwards' Clinical Affairs Department or authorized designee will conduct all aspects of data quality assurance (data monitoring, and monitoring of study sites) per departmental Standard Operating Procedures.

Each study site will adhere to all the requirements specified in this protocol. Assessments will be obtained for the preoperative and operative visits, and postoperatively at discharge, six months, 1-year and annually thereafter for a minimum of 8 years (see Tables 4, 5, 6 and 7).

The investigator will make every attempt to follow the subjects and will document the information gathered during the required study follow-up visits on the standardized CRFs. The subjects will be encouraged by the investigator to report any address or telephone number changes. They will also be informed of the importance of returning for scheduled follow-up visits even if they are not having any problems.

Each site will provide a list of normal blood values and a certificate, or equivalent documentation, outlining the quality level of their laboratory prior to study initiation.

# 6.1 **Preoperative Procedures**

All procedures shall be documented on the applicable visit case report forms (see Appendix 5). Compact discs or electronic copies of Doppler echocardiographic examinations will be sent directly to the Core Laboratory according to the procedures outlined in Appendix 3 - Echo Core Lab Protocol. A summary of all required treatment procedures can be found in Table - Study Schedule.

This document and the information contained herein is considered Proprietary and Confidential and may not be reproduced, used or disclosed without written permission from Edwards Lifesciences LLC.

Patient Status	Date of birth, gender, demographics		
Physical Assessment	Height, Weight, Heart Rate, Blood Pressure, NYHA classification		
Medical History	Non cardiac conditions, cardiac conditions, previous cardiac surgery		
Electrocardiogram	Cardiac Rhythm		
Blood studies 	RBC, WBC, HCT, Plasma Free HGB, (or Haptoglobin and SLDH) Platelet and Reticulocyte counts		
Pregnancy Test	Blood or Urine		
Medication Use	Antiplatelet, Antithrombolytic Therapies		
Coagulation Profile	PTT or INR		
Echocardiography 	Exam Date/Interval		
Echo Core Lab	Cardiac output, Ejection fraction, Peak and mean valve gradients, assessment of stenosis or regurgitation, LV structure and function, LV mass, jet velocities		
Quality of Life Survey 	EQ-5D		

#### Table 5: Pre- Operative Evaluations and Data Requirements

 Pre-procedure blood studies to be performed within 30 days of the planned valve replacement procedure.

 Pre- procedure echocardiography to be performed within 6 months of the planned valve replacement procedure

 Quality of Life survey to be completed within 3 months of planned valve replacement procedure

# 6.2 **Operative Procedures**

Investigators shall use routine surgical technique for mitral valve replacement surgery in accordance with the relevant IFUs and carefully following the valve sizing, and valve

orientation Tricentrix valve holder system instructions, (See Appendix 4 for Instructions for Use).

Required operative evaluations and data requirements are listed below in Table 6. An intra-operative transesophageal echo (TEE) is not required for this study, however if an echo is performed, the investigator should send a copy of the examination to the Echo Core Lab for evaluation.

Valve Implant Procedure	Implant date, implanting surgeon name		
Valvular Lesion Assessment	Diagnosis for valve replacement, current condition of valve, condition of annulus, (debridement procedures) condition of leaflets and preservation of subvalvular apparatus		
Study Valve Implant Data	Valve size, model and serial number, bypass pump time, total cross clamp time, suture technique, use of pledgets, valve seating leaflet coaptation		
Surgical Approach	Full or mini-sternotomy		
Concomitant Procedures	CABG, AVR, tricuspid repair, etc.		
Echocardiography	TEE is optional, If TEE is performed, site shall send to exam to Core Lab for evaluation		
Adverse Events	All adverse events or complications regardless of relationship to the device or valve replacement procedure		

#### Table 6: Operative Evaluations and Data Requirements

# 6.3 **Postoperative Procedures**

#### 6.1.1 Hospital Discharge

Prior to hospital discharge, the investigator or designee will provide the study subject with an Implant Data Card (See Section 10.8 and Appendix 7).

This document and the information contained herein is considered Proprietary and Confidential and may not be reproduced, used or disclosed without written permission from Edwards Lifesciences LLC.

The Investigator or designee will explain the use and importance of the implant card and shall ensure that all required information (Investigator Name, Facility Name and contact information) has been included on the card. The Investigator or designed shall also ensure that one of the valve serial number serial number stickers provided with the implant packaging is firmly attached to the back side of the Implant Data Card. The second implant serial number sticker should be placed either on the front page of the subject's operations notes, or scanned into the subject's hospital electronic records.

Hospital discharge evaluations and data requirements are listed in Table 7.

# Table 7: Early Post-Operative / Discharge Procedures and Data Requirements(30 days or discharge, whichever is later)

Patient Status	Complete Implant Card		
Physical Assessment	Heart Rate, Blood Pressure, NYHA		

	classification		
Electrocardiogram	Cardiac Rhythm		
Medication Use	Antiplatelet, Antithrombolytic Therapies		
Coagulation Profile	PTT or INR		
Echocardiography	Exam Date/Interval, clinical evidence of PV leak or regurgitation		
Echo Core Lab	Cardiac output, Ejection fraction, Peak and mean valve gradients, assessment of stenosis or regurgitation, LV structure and function, LV mass, jet velocities		
Adverse Events	All adverse events or complications that have occurred since the valve replacement procedure		

#### 6.1.2 Late Post-Operative Follow- Up

Postoperative follow-up visits are required between 3-6-months, at one year, and annually thereafter for a minimum of 8 years. Required evaluations and data requirements are listed below in Table 8.

Table 8. Late Post-Operative Procedures a	and Data Requirements
---	-----------------------

Patient Status	Visit Date, Type of Visit
----------------	---------------------------

Physical Assessment	Heart Rate, Blood Pressure, NYHA classification		
Electrocardiogram	Cardiac Rhythm		
Blood studies	RBC, WBC, HCT, Plasma Free HGB (or Haptoglobin and SLDH), Platelet and Reticulocyte counts		
Medication Use	Antiplatelet, Antithrombolytic Therapies		
Coagulation Profile	PTT or INR		
Echocardiography (6 mo, 1. 2, 4 6, and 8 year follow-up visits)	Exam Date/Interval, clinical evidence of PV leak or regurgitation		
Echo Core Lab	Cardiac output, Ejection fraction, Peak and mean valve gradients, assessment of stenosis or regurgitation, LV structure and function, LV mass, jet velocities		
Quality of Life Survey (6 month visit only)	EQ-5D		
Adverse Events	All adverse events or complications that have occurred since the last visit		

Echocardiography exams are required at the 6-month visit (between 3-6 months), and at 1, 2, 4, 6, and 8 year follow-ups ( $\pm$  1 month). A QOL survey (EQ-5D) will be completed for the 6-month follow-up visit.

Use of anticoagulant therapy is recommended for two to three months postoperatively except where contraindicated. The appropriate anticoagulation therapy must be determined by the physician on an individual basis and based on current ACC/AHA guidelines.

Clinical assessment of adverse events shall be conducted per revised STS guidelines (Appendix 1) and reported per the event classifications and definitions provided in Section 7.0 and Appendix 8 respectively.

This document and the information contained herein is considered Proprietary and Confidential and may not be reproduced, used or disclosed without written permission from Edwards Lifesciences LLC.

#### 6.4 Unscheduled Visits

If a subject needs to be seen at other than a regularly scheduled follow-up visit for assessment of cardiac symptoms, all visit information shall be recorded on the appropriate follow-up visit CRF. If blood studies are performed the investigator shall document these studies on the CRF. Doppler/echocardiography performed at these visits is optional, however if performed, the investigator should send the echo exam to the Core Lab for evaluation.

#### 6.5 Missed Visit

If a subject cannot be reached for the follow-up visit and misses the scheduled visit, the visit will be recorded as a missed visit. The study site shall document the efforts made to contact the study subject or the subject's primary health care provider for each required follow-up visit.

# 6.6 Lost To Follow-Up

A subject will be considered "lost to follow-up" and terminated from the study when all of the following criteria have been met:

- Failure to complete two consecutive visits without due cause; and
- Documentation of three unsuccessful attempts on three different days over a period of 3 months by the Investigator or his/her designee to contact the subject or next of kin; and
- A letter from the Investigator to Edwards requesting subject removal from the study, and
- Prior agreement of Edwards to remove the subject from the study.

This document and the information contained herein is considered Proprietary and Confidential and may not be reproduced, used or disclosed without written permission from Edwards Lifesciences LLC.

# 6.7 Time Periods for Completing Study Visits

Follow-up visits are scheduled for appointed times after the date of the procedure. It is important that this schedule be maintained as closely as possible for all study subjects. Edwards recognizes that subjects may not be able to return for all scheduled visits at precisely the date required, and therefore, a period of time in which each visit is allowed is described in Table 9 below. Studies not completed within these windows will be considered missed visits. Study visits should be scheduled as close to the early part of the visit time period as possible so that if it is necessary to cancel and reschedule the visit, the visit could still be conducted in the required time period.

Follow-up Visit	Time Period
Discharge/30 Days	Day before or Day of Discharge or 30 days post implant (whichever is later)
Early Postoperative	3 - 6 months
Late Postoperative	12 months ± 1 month
Late Postoperative	Annually from procedure date ± 1 month

Table 9. Schedule of Follow-up Visits and Time Periods

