## 9.2 Analysis Population

All the data collected up to the point of the explant or expirations will be included in the safety and effectiveness analyses. The primary safety analysis will include all the enrolled subjects. The primary effectiveness analysis will include the subjects who survived and have NYHA assessment at 8 years post implant.

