## 9.7 Missing Data

All statistical tests on the effectiveness endpoints will be performed in two ways: (1) using only those subjects with available required for endpoint analysis and (2) by using the method of last observation carried forward (LOCF). Both methods of analyses will then be compared. However, both methods will be used for the comparison of NYHA classification at 8 year post implant to OPC (75%) and for the comparison of hemodynamic performance one year to baseline for the purpose of investigating the effect of loss-to-follow-up.

NYHA classification and hemodynamic performance will be summarized at each of the follow-up interval. In addition, the NYHA classification will only be statistically compared to OPC at 8 years post implant and only the one year post implant hemodynamic performance will be statistically compared to baseline.

To further demonstrate the impact of lost of the follow-up on the effectiveness calculation; a bootstrapped simulation for missing data imputation will be generated as described below:

For each subject who is alive and for whom NYHA assessment is not available at the 8 year post implant follow up visit (Subject A), the last year for which NYHA data is available will be identified (year X).

This document and the information contained herein is considered Proprietary and Confidential and may not be reproduced, used or disclosed without written permission from Edwards Lifesciences LLC.

Separately, a sub group (Group A) of subjects with the same pre-operative and year X NYHA information as Subject A, available data at 8 year post-implant will be identified.

Subsequently, an observed value from the pool of subjects in sub group A will be selected randomly and used to impute the NYHA classification for subject A at 8 years post implant.

The above steps (1-3) will be performed for each subject who is lost to follow up before the 8 year post implant follow-up visit.

Lastly, steps 1 - 4 above will be repeated 999 times to generate 1000 estimated percentages of subjects with NYHA in classes I or II at 8 years post implant. The central 95th percentile for the 1000 estimated percentages will be calculated.

The central 95th percentile generated by the simulation will reflect the variability in the primary effectiveness endpoint estimate caused by lost to follow up.

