## White and Yellow: Return to Edwards Lifesciences, Clinical Affairs Pink: Retain for your Records

PROPRIETARY DATA: THIS DOCUMENT AND INFORMATION CONTAINED HEREIN MAY NOT BE REPRODUCED, USED, OR DISCLOSED WITHOUT WRITTEN PERMISSION OF EDWARDS LIFESCIENCES,											
HEART VALVE THERAPY GROUP, CLINICAL AFFAIRS DISCHARGE DATA REV E 2011											
	Clinical Review: Data Management:										
FOR	First Review:	Second Review: (optional)	First Data Entry:	Second Data Entry:	Subevent #						
EDWARDS	By:	By:	By:	By:	(optional)						
USE ONLY	Date:///	Date://	Date://	Date://							

Patient Study ID # 2 0 0 6 0 5	Clinic #
1. ASSESSMENT DATE:	
2. FOLLOW-UP INTERVAL:	
$\bigcirc$ 6 Month (3 – 6 months)	5 Years (59 – 61 months)
□ 1 Year (11 – 13 months)	6 Years (71 – 73 months)
2 Years (23 – 25 months)	7 Years (83 – 85 months)
3 Years (35 – 37 months)	8 Years (95 – 97 months)
☐ 4 Years (47 – 49 months)	Other, specify: Months Years

 
3. VISIT STATUS:
 
Conducted visit: (Check one only)
 
Office Visit / Clinic / Outpatient/ Ho
 
In-patient Admission
 
Phone (from whom):

	ospital īfy relationship īfy relationship
OR	
Missed visit: (Check Only One)	
Scheduled, patient missed	
Unable to contact patient	
Other ( Explain ):	
4. PATIENT STATUS:	
Explant (Complete explant,	adverse event and study exit form)
Death (Complete adverse e	vent and study exit form)
Withdrawn (Reason):	

Other, specify:

White and Yellow: Return to Edwards Lifesciences, Clinical Affairs Pink: Retain for your Records PROPRIETARY DATA: THIS DOCUMENT AND INFORMATION CONTAINED HEREIN MAY NOT BE REPRODUCED, USED, OR DISCLOSED WITHOUT WRITTEN PERMISSION OF EDWARDS LIFESCIENCES, HEART VALVE THERAPY GROUP, CLINICAL AFFAIRS ASSESSMENT DATA REV E 20110526

		HEART VALVE THERAFT GROUF,	CLINICAL AFFAIRS	ASSESSIVIENT DATA REVE 201	10520
	Clinical Review:		Data Management:		
FOR	First Review:	Second Review: (optional)	First Data Entry:	Second Data Entry:	Subevent #
EDWARDS	By:	By:	By:	By:	(optional)
USEONLY	Date:///	Date://	Date:///	Date:///	

Patient Study ID # 2 0 0 6 0 5	
ASSESSMENT DATE:	Y Y
5. PHYSICAL ASSESSMENT:	
Heart Rate (bpm)	
Weight (kg)	
Blood Pressure	mmHg
6. PREOPERATIVE CARDIAC RHYTHM (Check all that	apply) ECG
Not Done (Complete Protocol Deviation)	
Done Date:	Y Y Y
Normal Sinus  Atrial Fibrillation  A	trial Flutter
$\square$ AV Block (Indicate degree) $\square$ 1 s	$^{t}$ $\Box$ 2 nd $\Box$ 3 rd

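### The plan sets no analysis window for the 8-year NYHA endpoint, so the ±1 month missed-visit rule, read literally, sets aside real assessments made just outside 95–97 months

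*Combined protocol and SAP*

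**What the plan says.** **Visit rule.** Table 9 in Section 6.7 sets the annual window as "Annually from procedure date ± 1 month", and the text above it says "Studies not completed within these windows will be considered missed visits". The follow-up assessment form in Appendix 5 repeats the limits: the box for this visit begins "8 Years (95 – 97 months". The same form has a further box, "Other, specify: Months Years", so a value from 94 or 98 months can be recorded, but not under the 8-year label.

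**Primary effectiveness set.** Section 9.2: "The primary effectiveness analysis will include the subjects who survived and have NYHA assessment at 8 years post implant". Section 9.5.1 tests the class I/II percentage at 8 years against 75% with a one-sided exact binomial test. Neither section says in months what counts as 8 years.

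**General inclusion.** Section 9.2 also says: "All the data collected up to the point of the explant or expirations will be included in the safety and effectiveness analyses".

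**Missing data.** Section 9.7 plans an available-case analysis, a last-observation-carried-forward (LOCF) analysis, and a resampling exercise whose first step applies "For each subject who is alive and for whom NYHA assessment is not available at the 8 year post implant follow up visit". A later step in the same section describes the procedure as being for subjects lost to follow-up before that visit.

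**The concern.** The primary effectiveness endpoint is one NYHA class at one time point, eight years out. The only definition of that time point in the documents is the two-month visit window, and the rule attached to it relabels a late or early study as no visit at all. An analyst who follows the text would drop a subject seen at 98 months whose class is on file.

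Two things are at stake. The plan counts on 101 subjects with 8-year NYHA data, and enrolment was inflated for death and loss to follow-up but not for off-schedule attendance. And if subjects who attend off schedule differ in functional class from those who attend on time, leaving them out shifts the estimate. If the rule stays unsettled, the choice would be made after results are visible in a single-arm study.

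**Working it through.** **1. The plan's own figures.**
- NYHA power (Section 9.1: n=45, null 75%, expected 90%; one-sided α=0.05). The smallest rejecting count is 39 of 45, with exact α 0.0446 and power 0.841. This agrees with the stated 85% to within a point.
- Enrolment (Section 9.1: 8-year survival 56%). With n=212, P(X > 101) = 0.991, above the stated 98.7%. Inflating for 15% loss: 212/(1 − 0.15) = 249.4, rounded up to 250.

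Both reproduce. No sample-size figure is in dispute here.

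**2. Following a 98-month assessment through the text.**
- Section 6.7: outside 95–97 months, so a missed visit.
- Section 9.2: the primary set takes those who have an assessment at 8 years. If the visit is missed, the subject is out. Nothing is imputed in this analysis.
- Section 9.7, LOCF: a 98-month value lies after the target, and the text does not say it may be used. Ordinary LOCF would carry an earlier one. A 94-month value lies before the target and could itself be carried forward, so it would be kept.
- Section 9.7, resampling: the first step is met on its wording, so another subject's value could be drawn. The later limitation to subjects lost to follow-up points the other way.

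**3. Expected size of the 8-year set.** The formula is 250 × 0.56 × (1 − loss) × (1 − f), where f is the share of assessments outside the window. The documents give no value for f, so a range is assumed. Loss is 15% (the planning allowance) or 7.8% (observed in the sponsor's earlier study, Section 9.1). Survival, retention and timing are taken as independent.

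| f (assumed) | 15% loss: expected n | P(≥101) | 7.8% loss: expected n | P(≥101) |
|---|---|---|---|---|
| 0 | 119 | 0.991 | 129 | 0.9999 |
| 10% | 107 | 0.800 | 116 | 0.977 |
| 20% | 95 | 0.244 | 103 | 0.638 |
| 30% | 83 | 0.011 | 90 | not computed |

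**4. Power of the NYHA test if subjects are lost from 101** (exact one-sided test, 75% against 90%).

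| n | Rejecting count | Power |
|---|---|---|
| 101 | 84 | 0.989 |
| 91 | 76 | 0.982 |
| 81 | 68 | 0.971 |
| 71 | 60 | 0.952 |
| 50 | 43 | 0.878 |

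**5. Illustrative selection effect.** Suppose 90% of in-window and 75% of out-of-window subjects are in class I/II (both assumed). The complete-case estimate is then too high by 0.90 − [(1 − f) × 0.90 + f × 0.75] = 0.15f, that is 1.5 points at f=10% and 3.0 points at f=20%.

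**The case against.** The strongest reply is that exclusion is inferred. Section 6.7 governs visit conduct, Section 9 never refers to it, and Section 10.6.1 treats noncompliance with follow-up visits as a documented deviation, not a reason to delete data. The general sentence in Section 9.2 and the free-text interval on the form suggest that such values are meant to be kept. This stands in part: no analysis rule says that out-of-window values are discarded. But the general sentence only sets a cut-off at explant or death. It does not assign a value to a time point, and the same section then restricts the primary set to those assessed at 8 years.

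A reader might also infer more than the text supports:
- *That the primary analysis replaces real values by imputed ones.* It does not, because it is complete-case.
- *That LOCF overrides every off-window value.* A 94-month value could be the one carried forward.
- *That resampling would certainly apply.* Section 6.6 requires two consecutive missed visits, three failed contact attempts, an investigator's letter and sponsor agreement before a subject counts as lost to follow-up. Someone seen at 98 months would not ordinarily qualify, so only the first step of Section 9.7, taken alone, reaches that subject.
- *That earlier missing data show what the window will cost.* Appendix 9 lists NYHA as unavailable at year 5 in 63 of 129 (48.8%) and 27 of 96 (28.1%) subjects in the two predecessor data sets. No reasons are given, so these figures show that completeness is fragile, not that timing caused the gaps.

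**Conclusion.** The point holds as a defect in the definition of the primary effectiveness endpoint. The only stated window is 95–97 months, studies outside it are called missed, and nothing in Section 9 recovers them.

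Its size depends on an out-of-window rate that the documents do not give. At an assumed 20%, the expected set is 95 or 103 depending on the loss rate, so whether the 101 is met turns on assumptions. A reader might conclude that the test would be underpowered. The figures do not support that: power is still 0.88 with about half of the 101 lost. What remains is the needless loss of valid primary-endpoint data and a selection effect of unknown direction and size. That off-schedule attenders are sicker is a possibility, not something the documents show. This is a worthwhile, inexpensive improvement and not a threat to the study's validity.

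**What to change.** - **Section 6.7:** leave ±1 month in place as the standard for visit compliance and deviation reporting.
- **Sections 9.2 and 9.5.1:** define the 8-year NYHA as the assessment closest to 96 months within a pre-specified analysis window that does not overlap those of neighbouring years. A range of 90–102 months is one example, since it reaches halfway to the 7- and 9-year anniversaries. State a rule for ties and for values falling on a boundary.
- **Sensitivity analysis:** repeat the test on the strict 95–97 month set and report how many subjects each definition contains.
- **Section 9.7:** apply LOCF or resampling only when no assessment falls in the analysis window, and reconcile the two descriptions of whom the resampling covers.

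The cost is a few lines of SAP text, with no new data and no change to conduct. Assessment times will be slightly more spread out. That matters little, because Section 9.1 says the class I/II proportion in the predecessor valve hardly varied from one annual visit to the next.
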